- Aim 2: Explore whether the effects of sPI are mediated by changes in sleep, depressive symptoms, activity circadian rhythms, melatonin and/or inflammatory markers.** Hypothesis 2a: The effects of sPI on CRF are mediated by changes in sleep quality. Hypothesis 2b: The effects of sPI on CRF are mediated by changes in depressive symptoms. Hypothesis 2c: The effects of sPI on CRF are mediated by changes in activity circadian rhythms (measured via actigraphy and melatonin rhythmicity). Hypothesis 2d: the effects of sPI on CRF are mediated by changes in inflammatory markers. **Aim 3: Determine the feasibility and acceptability of sPI, actigraphy, urine collection and monitoring of light exposure.** Hypothesis 3a: Initiating the sPI environment in patient hospital rooms during inpatient procedures (HSCT and initial chemotherapy regimen to treat MM and related oncological diseases) will be tolerable among MM-HSCT patients and medical professionals. Hypothesis 3b: sPI will be feasible as an inpatient treatment method to prevent common circadian rhythm-based side effects observed with HSCT and subsequent chemotherapy. Hypothesis 3c: sPI implementation inpatient hospital rooms will maximize potential patient benefit while minimizing deviation from normal lighting fixture end-user experience for both HSCT patients and medical professionals. Hypothesis 3d: Actigraphy collection among HSCT patients will be acceptable as an assessment method before, during, and after HSCT. Hypothesis 3e: Urine collection among HSCT patients will be tolerable as an assessment method before and during hospital visit for HSCT. Hypothesis 3f: Monitoring of light exposure via Daysimeter data among HSCT patients will be acceptable as an assessment method before and during HSCT.

2) Background

Debilitating fatigue – a persistent sense of exhaustion frequently associated with a number of serious medical conditions, including cancer – can interfere with mood, activities of daily living, treatment compliance. Such fatigue is often associated with sleep problems, depression, quality of life, and agitation. Unfortunately, currently available interventions for CRF are, at best, only modestly effective. Pharmacological agents have been studied for CRF, but there is insufficient evidence to recommend their use. Non-pharmacological interventions have shown clinical benefit, but they can be labor-intensive, expensive, and cumbersome for patients. A promising alternative is light therapy.

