With regard to safety endpoints, there are no known major risks associated with the use of bright white light in the treatment of either fatigue or depression. However, we will monitor those who decide to cease treatment because they find the treatment approach unacceptable along with their concerns regarding treatment.

e) Procedures Involved in the Human Research

Approach: We will explore the acceptability, feasibility and potential efficacy of sPI exposure to prevent CRF in patients undergoing initial autologous HSCT, as provided during their inpatient hospital stay for approximately two weeks following transplant. We will also determine the feasibility of investigating biological markers (i.e. melatonin, inflammatory markers) as mediators of the clinical impact on CRF. Urine samples will be collected at two timepoints to assess melatonin rhythmicity. Blood samples will be collected at four timepoints to assess the inflammatory response in relationship to the light treatment.

The proposed approach will be informed by procedures [name] developed for her recent research on sLE treatment in Alzheimer's patients. Additionally, we will be building on our previously established protocols to inform our ability to research sPI treatment. The two teams of investigators will work closely, carrying out weekly conference calls and quarterly face-to-face meetings alternating between MSH and Rensselaer Polytechnic Institute (RPI). The MSH team will recruit study participants and oversee use of the light fixtures, monitoring equipment, assessment scales, and facilitate with [name]'s laboratory regarding proper storage and analysis of urine samples. MSH will also collaborate with the Mount Sinai's Human

	Protocol Name:	Systematic Programmed Illumination of Hospital Rooms to Prevent/Reduce Cancer-Related Fatigue during Autologous Stem Cell Transplantation for Multiple Myeloma
	Principal Investigator:	[name]; [contact]
	Primary Contact Name/Contact Info:	[name], [contact], [contact]
	Date Revised:	8/15/2019
	Study Number:	IF# 2517160 HS# 15-00777 GCO#: 15-2009

Immune Monitoring Core Shared Resource Facility at Mount Sinai to process and analyze blood samples to assess and track inflammatory markers.

Actigraphs will be used to monitor bio-behavioral indicators of circadian rhythms. The Actigraph is attached to the non-dominant wrist and measures movement and activity. The Daysimeter is worn around the neck and measures light exposure.

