The proposed research is a low-risk behavioral trial. Study staff will be available to participants who have any difficulty with their equipment or any unexpected reaction during the intervention period. Study staff will be required to report all serious adverse events (SAEs) to the Mount Sinai IRB according to policies and procedures outlined by that body. Study staff members are also responsible to report all SAEs to the study PI as well. As per Icahn School of Medicine at Mount Sinai's IRB policies, the study PI is required to notify the IRB promptly of any unanticipated problems involving SAEs and risks to subjects or others that occur. The study staff PIs will monitor the progress of the trial and safety of participants on an ongoing basis. The procedures of this study will ensure discussion and reporting of all possible outcomes including adverse events. If the adverse event is due to the intervention and is unexpected, the PI will draft a safety report and send a copy to the Mount Sinai IRB. The IRB committee will serve as an objective review mechanism. This policy/procedure means that any potential conflict of interest inherent in the PI being the sole reviewer of SAEs is avoided.

We will use screening procedures from our prior grants to assess depression/suicidality. If risk of suicidality or severe depression is revealed, a licensed clinical psychologist in New York State, will contact the participants the same day, taking emergency steps and making referrals as needed.

2. Plans for assuring adherence with requirements regarding the reporting of adverse events (AEs).

All serious AEs (e.g., medical occurrences resulting in either hospitalization or death) that occur during the study defined by the given protocol, regardless of the relation to the research, must be reported to the IRB by telephone, e-mail or fax within 24 hours of the investigator's awareness of the occurrence of the

	Protocol Name:	Systematic Programmed Illumination of Hospital Rooms to Prevent/Reduce Cancer-Related Fatigue during Autologous Stem Cell Transplantation for Multiple Myeloma
	Principal Investigator:	[name]; [contact]
	Primary Contact Name/Contact Info:	[name], [contact], [contact]
	Date Revised:	8/15/2019
	Study Number:	IF# 2517160 HS# 15-00777 GCO#: 15-2009

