event. The PI will report SAEs to the Mount Sinai IRB and will disseminate information to other sites or agencies as necessary. These safety reports are a written account of an SAE determined by the PI to be both related to the psychological treatment under investigation and unexpected in nature. Serious AEs will be summarized annually in the IRB application for continuation or termination of research.

All expected non-serious AEs that occur at a greater frequency or severity than anticipated and all unexpected non-serious AEs will be reported to the Mount Sinai IRB within 15 working days of the PI becoming aware of the event. Adverse events that will be reported include suicidal ideation, which will be monitored at each check-in. These AEs are also summarized annually in the IRB application for continuation or termination of the research.

3. Plans for assuring that any action resulting in a temporary or permanent suspension of an NCI-funded clinical trial is reported to the NCI grant program director responsible for the grant.

The Director of the Grants and Contracts Office at Icahn School of Medicine at Mount Sinai will provide prompt written notification of any action resulting in a temporary or permanent suspension of this protocol to the NCI grant program director responsible for the grant.

4. Plans for assuring data accuracy and protocol adherence.

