The proposed intervention is low-risk, and has been heavily informed by prior investigation by [name] and [name] . They are familiar with the intervention and its potential side effects, and will be able to provide consistent oversight of the project. Coherence of the collected data will be assessed on a yearly basis, while treatment compliance, adverse events, and patient expectancy/blinding will be assessed once every three months by [name], [name] and research coordinators. They will inform and alter study methods based on this information. Data management is described in section h above. If the study is put on hold, IRB will be informed of the change in study timeline.

i) Withdrawal of Subjects

Patients will be allowed to withdraw from the research at any time. They will also be allowed to skip any questions or questionnaires.

6) Risks to Subjects

There always exists the potential for loss of private information; however, all possible precautions will be set in place in order to prevent loss of confidentiality. See section 5h.

Other risks or side effects may include:

- Headache
- Nausea

	Protocol Name:	Systematic Programmed Illumination of Hospital Rooms to Prevent/Reduce Cancer-Related Fatigue during Autologous Stem Cell Transplantation for Multiple Myeloma
	Principal Investigator:	[name]; [contact]
	Primary Contact Name/Contact Info:	[name], [contact], [contact]
	Date Revised:	8/15/2019
	Study Number:	IF# 2517160 HS# 15-00777 GCO#: 15-2009

- If used incorrectly (e.g. such as staring directly into the light) it may cause eye discomfort or eye strain
- **Likelihood of Harm:** There will be minimal risk to the participants. Light levels will be much lower than those experienced when subjects are outdoors during a bright sunny day. The subjects will not be exposed to ultraviolet radiation.
- Light levels used in this experiment are lower than the levels produced by typical bright-light boxes (which is 10,000 lux) or produced at midday in a clear sunny day (about 100,000 lux). Using hazardous light exposure levels specified by the American Conference of Government Industrial Hygienists, one would need to be exposed to this light source for more than 10 hours continuously before it becomes a risk.

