- Major research has not found increased risks of using light therapy for most major eye diseases. However, in the unlikely event the participant feels that the light is affecting their eyes or vision, they will be advised to contact the research team immediately.
- Previous research suggests that light therapy can improve the effectiveness of some antidepressant drugs. No evidence to date suggests that it decreases the effectiveness. If the participant is concerned about this, they will be advised to consult their physician.
- Completing questionnaires during the study may cause some distress or discomfort, however, past research has shown that such distress is usually minimal and transient.
- Wearing the light monitor (Daysimeter) and/or activity monitor (Actigraph) may cause discomfort. If this discomfort is unmanageable, the participant will be asked to report such discomfort to the research coordinator.
- Risks associated with blood draws: There is a minimal risk of pain, bruising, swelling, dizziness, or infection when blood is drawn from your arm. Some people feel dizzy or may faint during or after a blood draw. To minimize risk, blood for research purposes will only be drawn at the same time as routine clinical blood draws.

7) Provisions for Research Related Harm/Injury

The proposed project is a low-risk behavioral study. We will inform participants during the consent process that there is a chance that they will experience potential side effects of light therapy, e.g., sleep disturbance, headache, eyestrain, nausea, and hyperactivity, and in very rare instances, photic maculopathy, photophobia, hypomania, and suicidal ideation/suicide attempts have occurred (in those with pre-existing severe depression). They will be informed that such side effects are usually minimal if the light is positioned correctly and when they do occur, resolve within a few days. During the course of the protocol, if after 3 days the side effects persist, we will withdraw them from the study. Additionally, their care provider at the BMT clinic will be notified and refer the patient to a specialist if necessary. We will also follow up with those who discontinue the study due to side-effects and refer them to their care provider should symptoms persist even after discontinuation of the light exposure. Medical concerns will be billed according to other procedures occurring during hospitalization, since this is an inpatient study.

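### The stated safety endpoint counts only patients who choose to stop the light, and most of the side effects the protocol names have no described means of collection or comparison by arm

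*Combined protocol and SAP*

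**What the plan says.** All references are to the combined protocol and SAP.

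- **Safety endpoint (section 5d, Endpoints).** After noting that bright light has no known major risks, the plan states: "we will monitor those who decide to cease treatment because they find the treatment approach unacceptable along with their concerns regarding treatment". No other text is presented as a safety endpoint.
- **Named side effects (section 7).** The consent discussion will cover "sleep disturbance, headache, eyestrain, nausea, and hyperactivity, and in very rare instances, photic maculopathy, photophobia, hypomania, and suicidal ideation/suicide attempts have occurred". Section 6 also lists headache, nausea and eye discomfort or strain.
- **Withdrawal by staff (section 7).** "if after 3 days the side effects persist, we will withdraw them from the study".
- **Detection (Data, Safety, and Monitoring Plan, item 1).** "Study staff will be available to participants who have any difficulty with their equipment or any unexpected reaction during the intervention period".
- **Reporting (same plan, item 2).** "All expected non-serious AEs that occur at a greater frequency or severity than anticipated and all unexpected non-serious AEs will be reported" to the IRB. No anticipated frequency is given.
- **Review (section 5h).** "treatment compliance, adverse events, and patient expectancy/blinding will be assessed once every three months".
- **Tolerability (section 1, Hypothesis 3a).** The light environment "will be tolerable among MM-HSCT patients and medical professionals". No criterion is attached. The Data Analysis text gives models for Aims 1 and 2 and none for Aim 3 or for safety.

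**The concern.** A patient who has headaches or eyestrain under the light and puts up with them never enters the stated endpoint. Nor, on the wording, does a patient whom staff take off study because side effects persist, since that patient did not decide to stop. Section 7 itself says that side effects usually settle within a few days. Short-lived effects in patients who continue are therefore what the protocol expects most often, and they are what this endpoint misses.

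Tolerability is an explicit aim of a trial that calls itself a feasibility study. If it is read from the stated endpoint, the error runs in one direction: towards a cleaner picture than the true one. The trial also has a randomised dim-light arm against which side effects could be compared, but the plan neither collects most of them systematically nor says they will be tabulated by arm.

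**Working it through.** **1. Who is counted.**

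| Patient | Counted by the 5d endpoint as worded? |
|---|---|
| Side effect, continues with the light | No |
| Side effect, decides to stop because treatment is unacceptable | Yes |
| Side effect persists, withdrawn by staff (section 7) | No |

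**2. Which named effects have a described means of collection.** Section 7 names nine: five common, four rare.

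| Effect | Described collection |
|---|---|
| Sleep disturbance | Pittsburgh index and actigraphy, with baseline values |
| Suicidal ideation or attempts | BDI-II question 9 (section 5a); ideation also at check-ins (monitoring plan, item 2) |
| Headache, nausea, eyestrain, hyperactivity | None described |
| Photic maculopathy, photophobia, hypomania | None described |

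Seven of the nine have none. Among the instruments in section 5e, the one listed under symptom measures is the BSI-18, presented as a measure of psychological distress. The FACIT-TS-G (section 5d) measures satisfaction. The medical tracking form is not described as having a field for side effects of the light.

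**3. Size of the undercount.** The plan has no figure to reproduce. The only input from it is 30 patients per group (Data Analysis, Power). Two quantities are assumed: p, the share of active-arm patients with a side effect, and s, the share of those who choose to stop. Patients are taken as independent, and unaffected patients as not stopping.

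Affected = 30p. Expected count on the 5d endpoint = 30ps. P(none counted) = (1 − ps)^30.

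| p | Affected | s = 0.05: count, P(0) | s = 0.25: count, P(0) | s = 0.50: count, P(0) |
|---|---|---|---|---|
| 0.10 | 3 | 0.15, 0.860 | 0.75, 0.468 | 1.5, 0.215 |
| 0.20 | 6 | 0.3, 0.740 | 1.5, 0.215 | 3.0, 0.042 |
| 0.40 | 12 | 0.6, 0.545 | 3.0, 0.042 | 6.0, 0.001 |

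For example, at p = 0.20 and s = 0.25, ps = 0.05, 30 × 0.05 = 1.5 and 0.95^30 = 0.215. The undercount vanishes only at s = 1, when every affected patient chooses to stop.

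**4. What zero events would mean.** With complete ascertainment, 0/30 has a two-sided 95% upper limit of 1 − 0.025^(1/30) = 11.6%. At the 71% retention that section 2 expects, 30 × 0.71 = 21.3, and 0/21 gives 1 − 0.025^(1/21) = 16.1%. The same zero on the stated endpoint bounds the rate of choosing to stop, not the rate of side effects.

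**5. What a comparison by arm could show.** Power at two-sided 0.05 for assumed rates, by normal approximation with pooled null variance: Φ{(|p1 − p0| − 1.96√[2p̄(1 − p̄)/n]) / √[(p0(1 − p0) + p1(1 − p1))/n]}. Exact Fisher power is in brackets.

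| Rates | n = 30 per arm | n = 21 per arm |
|---|---|---|
| 10% v 30% | 0.49 (0.37) | 0.36 (0.26) |
| 20% v 40% | 0.39 (0.30) | 0.29 (0.19) |
| 30% v 60% | 0.65 (0.56) | 0.50 (0.36) |

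A test would usually miss even large differences, so rates with confidence intervals are the right output.

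**The case against.** The best defence is that one sentence in section 5d is not the whole safety system. Serious events go to the IRB within 24 hours, and unexpected non-serious events within 15 working days. Adverse events are reviewed quarterly, patients who leave because of side effects are followed up, and the 3-day rule presupposes that staff notice side effects in patients still under the light. All of this stands, and a reader who inferred that the trial has no safety monitoring would be wrong. These are duties to report, review and manage, however. No form, schedule, grading or tabulation by arm is described, and expected events at or below an unstated anticipated level need not be reported.

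Three stronger readings are tempting, and the documents do not support them.

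- **That no instrument records any named side effect.** Sleep disturbance and suicidal ideation are covered, the former with values before the light starts. For the other seven, the items of the scales are not reproduced, so the most that can be said is that no instrument is described as recording them.
- **That effects of the light could not be told from transplant symptoms.** Both arms undergo transplant, and randomisation would separate the two on average if side effects were solicited equally. The gap lies in collection and analysis, not in the design. The documents do not say how often headache or nausea arises from transplant.
- **That section 5d is the designated measure of Hypothesis 3a.** No text makes it so, and satisfaction scores and the acceptability assessment also bear on tolerability. The bias therefore arises to the extent that tolerability is judged on the stated endpoint.

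**Conclusion.** The point holds in this form. The one stated safety endpoint follows only patients who choose to stop. It omits side effects in those who continue and, as worded, withdrawals initiated by staff. Seven of the nine effects named in section 7 have no described collection, and none of the adverse event provisions calls for solicitation or comparison by arm. Tolerability judged on that endpoint would tend to look better than it is.

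The direction follows from the wording. The size does not, because the documents give no side-effect or stopping rates. Under the assumed values, the expected count is between 5% and 50% of the affected patients (the assumed s), and the chance of counting nobody runs from 0.001 to 0.860. The efficacy comparison is not affected. The change should be made, since tolerability is a stated aim and the cost is small.

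**What to change.** 1. Replace the safety endpoint in section 5d with a safety and tolerability endpoint: the incidence by arm of each side effect named in sections 6 and 7, plus all discontinuations, each with its reason and whether the patient or staff initiated it. Reconcile sections 5d and 7 on which discontinuations count. No change to the withdrawal rule itself is proposed.
2. Collect the seven effects that lack an instrument on a short yes/no and severity checklist, identical in both arms, once before the first light and then with the daily Fatigue Line Scale already given in hospital. Keep the existing sources for sleep disturbance and suicidal ideation.
3. At final analysis, report rates by arm with confidence intervals, without tests. For scale, at 10% v 30% with 30 per arm the standard error of the difference is √[(0.09 + 0.21)/30] = 0.10, a 95% half-width of about 20 percentage points.

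Two additions should be avoided. Using the comparison-arm frequency as the anticipated level in the reporting rule would fire by chance: with equal true rates of 20% and 30 per arm, the active count exceeds the other with probability about 0.44 per effect, and 1 − 0.56^5 ≈ 0.94 for at least one of five independent effects. Tables by arm at the three-monthly review risk unblinding the team, which may alter study methods on what it sees.

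The cost is protocol wording and about a minute of patient time a day. Solicited events will be more numerous than spontaneous reports, which the final report should say.

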- The Pittsburgh Sleep Quality Index – The Pittsburgh Sleep Quality Index consists of 19 self-rated items. Scale reliability is excellent using both an internal consistency criterion (Cronbach's alpha = 0.83) and test-retest reliability (r = 0.85). The validity of the instrument is based on its ability to discriminate patients (those having either sleep problems and/or depressive symptoms) from controls (healthy participants without sleep complaints).
- SF-36 scale - Quality of life will be assessed using the SF-36 scale. The SF-36 is a multi-purpose, short form health survey consisting of 36 questions. Both test-retest and internal consistency reliability exceeded 0.70 in studies of this scale's psychometric properties. The scale also has demonstrated content, criterion, and predictive validity.

Depression Measures:

- CES-D (Center for Epidemiologic Studies Depression Scale) – 20 item questionnaire that comprise six scales reflecting major dimensions of depression: depressed mood; feelings of guilt and worthlessness; feelings of helplessness and hopelessness; psychomotor retardation; loss of appetite; and sleep disturbance. The CES-D has been shown to be a reliable measure for assessing the number, types, and duration of depressive symptoms across racial, gender, and age categories (Cronbach's alpha \geq 0.80). Concurrent validity by clinical and self-report criteria, as well as substantial evidence of construct validity has been demonstrated.

Emotion Measures:

- PANAS – The Positive and Negative Affect Schedule (PANAS) is a 20-item self-report measure of positive and negative affect developed by Watson, Clark, and Tellegen (1988). NA and PA reflect "dispositional imensions, with high-NA epitomized by subjective distress and unpleasurable engagement, and low NA by the absence of these feelings." Conversely, PA represents the extent to which an individual experiences pleasurable engagement with the environment. Consequently, emotions such as enthusiasm and

	Protocol Name:	Systematic Programmed Illumination of Hospital Rooms to Prevent/Reduce Cancer-Related Fatigue during Autologous Stem Cell Transplantation for Multiple Myeloma
	Principal Investigator:	[name]; [contact]
	Primary Contact Name/Contact Info:	[name], [contact], [contact]
	Date Revised:	8/15/2019
	Study Number:	IF# 2517160 HS# 15-00777 GCO#: 15-2009

alertness are indicative of high PA, whilst lethargy and sadness characterize low PA. Both the PA and NA have decent Test-retest reliability ($r=0.68$ and $r=0.71$ respectively) and decent Internal Consistency (Cronbach's $\alpha = 0.87$).

Symptom Measures:

- **Brief Symptoms Inventory-18 (BSI-18)** - BSI-18 is one an integrated series of instruments designed to measure psychological distress. A more concise version of the 53 item BSI, the BSI-18 boasts 18 items and, according to its authors, this inventory presents satisfactory reliability indexes, both for the dimensions (ranging from .74 to .84) and the general distress index (.89). It has decent Test-retest Reliability ($r=0.76$) and good Internal Consistency (Cronbach's $\alpha = 0.89$).

Medical tracking form - Medical data will be gathered through medical chart review and interview including comorbid and excluded medical conditions, medical information related to transplant, current prescription sleep-related and non-sleep-related medications, history of treatment with light therapy, and remaining exclusion criteria. During the final timepoint, research coordinators will check the participant's medical chart using the medical tracking form and enter updated relevant health information into a password protected file.

f) Specimen Banking

Urine Samples –

All 60 participants will be assessed using biological measures (via urine samples) at two points. Samples will be collected once during baseline 1 before their transplant admission and once during inpatient treatment (on Day Three of engraftment)..

Outpatient urinary samples will be collected at home by the participant, according to the provided timetable. Exact times will be noted on the samples in case of any variance in sample timing. Participants will be instructed to collect any void after 11pm up to 1st AM void overnight during the 72-hour span of wearing the actigraph and daysimeter at baseline, and then during hospitalization prior to discharge. Urinary sample containers will be provided by the study team. Collection time of samples will be written on the outside of the containers by participants. Samples will be refrigerated and mailed directly to RPI LRC Biomarker Lab for analysis using a pre-paid shipping label provided by RPI.

Biological samples collected in the hospital will be gathered according to regular BMT procedures by a registered nurse or physician, and processed as with at-home collections.

Blood samples –

	Protocol Name:	Systematic Programmed Illumination of Hospital Rooms to Prevent/Reduce Cancer-Related Fatigue during Autologous Stem Cell Transplantation for Multiple Myeloma
	Principal Investigator:	[name]; [contact]
	Primary Contact Name/Contact Info:	[name], [contact], [contact]
	Date Revised:	8/15/2019
	Study Number:	IF# 2517160 HS# 15-00777 GCO#: 15-2009

Research related blood draws will be performed at four time points corresponding with routine clinical blood draws: First blood draw upon admission to the hospital, at the third day of engraftment (T3e, at the clinical visit about one month post-transplant (T4) and at the clinical visit about three months post-transplant (T5). Blood will be collected at MSH by a licensed phlebotomist. At each time point 16.7mL (approximately 3.5 teaspoons) will be collected in red top SST tubes, yellow top ACD tubes, and blue top Tempus tubes, delivered within 30 minutes, and processed immediately in the laboratories of Mount Sinai's Human Immune Monitoring Core Shared Resource Facility according to established blood processing protocols.

g) Data Management and Confidentiality

All data obtained will be placed into individual research participant folders and stored in a locked file cabinet in the department of Oncological Sciences. Only study personnel will have access to this file cabinet. All folders and data pertaining to individual subjects will be identified only by a code number and only the PI ([name]) and Co-investigator ([name]) the research coordinators will have access to electronic file that links the numbers to patient identities. Upon completion of the study, the file that links patients to the codes will be deleted.

Data sent between RPI, Mount Sinai, and the participants will be shipped via UPS. Patient names and dates of birth will not be included in mailed data to protect patient privacy. Mailed data will only be identified with study-ID numbers. RPI will be assessing melatonin levels, and will not receive any protected health information (PHI) other than the results of the biological assessments as well as assessments taken over the course of the study.

Data from any web-based assessment tools will be accessible to research study team using password protection and will only be identified by participant ID number. Paper files and printouts of assessment scores will be kept in a locked cabinet with access only by authorized project research staff. The use of email will be in accordance with MSH policy (i.e. secure email, obtaining consent from subject to send email, etc.).

Urine and blood samples will be marked only by study ID number and no other identifying information.

Data Analysis:

Descriptive statistics will be calculated both for the entire group and separately for each treatment group. T-tests and Fisher's exact tests will be used to assess group differences at baseline for possible confounders (i.e., demographic variables, clinical characteristics, and medications). Any variables showing differences between the two groups will be used as covariates in subsequent analyses. Since there is no known seasonality effect to measures of fatigue or to measures of sleep, which are our main outcome measures, seasonality will not be controlled in these analyses. For the primary outcome (Fatigue), the secondary outcomes (Depression, Sleep, Circadian Activity Rhythms, melatonin (exploratory), and Quality

	Protocol Name:	Systematic Programmed Illumination of Hospital Rooms to Prevent/Reduce Cancer-Related Fatigue during Autologous Stem Cell Transplantation for Multiple Myeloma
	Principal Investigator:	[name]; [contact]
	Primary Contact Name/Contact Info:	[name], [contact], [contact]
	Date Revised:	8/15/2019
	Study Number:	IF# 2517160 HS# 15-00777 GCO#: 15-2009

of Life), hierarchical random effects linear mixed models will be employed for Aims 1 and 2 using MIXED with repeated measures. Besides time (linear and possibly quadratic trends to allow for possible nonlinear trends), any covariates identified in the preliminary analyses and intervention group will be assessed in a fixed effects model. Each model will also include a random intercept. Post-hoc comparisons will be Tukey-adjusted. Since there are multiple secondary outcomes, the p-values will be Sidak adjusted for correlated multiple comparisons. Any variations in length of hospital stay (i.e., length of intervention) will be used as a covariate in all analyses. This is highly unexpected since 90% of ASCT patients are hospitalized for 14 days. In the Analysis of Aim 2, we will establish that the treatment is a significant predictor of the primary outcome (CRF) as well as the hypothesized mediators. Next, we will first examine the role of each of the mediators of the effects of sPI on CRF by introducing each individually into the equation which contains the time variable, the treatment main effect, and the time by treatment interaction. Each mediator which is a significant predictor of CRF in this equation will then be combined with any other significant mediating predictor of CRF into a single equation. We predict the introduction of each significant mediator will result in the decrease in the significance of the time by treatment interaction effect on CRF. However, the more important test of the mediating role by any variable will depend on the statistical significance of the indirect path from treatment to mediator and from mediator to the outcome. Following procedures suggested by Shrout and Bolger (2002), 1000 bootstrap samples will be employed to determine the significance of each indirect path.⁵⁰ **Power:** It is difficult to discuss power for **Aim 1** and **Aim 2** since there is no directly relevant past research. As a consequence, one of the goals of this project is to obtain estimates of the effect sizes that will eventuate from our proposed analyses. Although unknown at the moment, these effect sizes can guide decisions regarding sample sizes for a larger scale grant. In the interim, there are three lines of research that may provide some guidance. The first involves the work of [name], who investigated the effects of light treatment on fatigue experienced by women undergoing chemotherapy for breast cancer.⁹ Using her results, we calculated power for a repeated measures design with an autoregressive lag 1 structure and autocorrelations ranging from 0.40 to 0.60. With alpha equal to 0.05 and a sample size of 30 patients per group, power ranged between 0.96 and 0.98. We followed a similar approach using [name]'s results but focusing only on MM survivors of ASCT.¹⁰ In this case, power was 0.99 for autocorrelations ranging between 0.40 and 0.60. However, the latter results must be treated cautiously because these calculations were based on a very small sample (N = 17 survivors). Using the same small sample, our repeated measures analysis of depression indicated that the time by treatment condition interaction was marginally significant (p = 0.0568). The F-ratio for this interaction yielded an eta coefficient of 0.48 which would be considered moderately strong following Cohen's criteria.⁴⁹ We hypothesize that the interaction effect would have been significant had the sample size been larger as is being proposed in this study (N = 60). Because of the very small survivors sample and the variability of our indicator of circadian activity rhythms (the f-statistic), the Mixed program did not converge and it was not possible to obtain a power estimate for this outcome. The third line of research that is germane to power in the proposed pilot study was conducted by Sim and Lewis who applied the UCL approach and found that a pilot sample of n => 55 would minimize the overall sample size for small to medium standardized effect sizes (0.2-0.6).
